Title: The use of a routine indwelling urinary catheter in patients receiving neuraxial anesthesia for elective total joint arthroplasty

PI: [name] [name]

Co-investigators:

[name]

[name]

[name]

[name], BS

IRB Approval # 19123101

NCT #05428020

Document attached: Study protocol

Approved study: 2/21/2020

Approved amended protocol: 10/7/20

ORA: 19123101-IRB03 Date IRB Approved: 2/21/2020 Amendment Date: 10/7/2020

The use of a routine indwelling urinary catheter in patients receiving neuraxial anesthesia for elective total joint arthroplasty

Principal Investigator [name] M.D

Co-Investigators
[name] M.D
[name] M.D
[name] M.D
[name]

Purpose:

Determine whether routine use of a short term indwelling urinary catheter decreases the rate of urinary retention in patients undergoing elective inpatient total joint replacements

Hypothesis:

We hypothesize that the routine use of a short term indwelling urinary catheter will decrease the rate of urinary retention compared to patients who do not receive a urinary catheter.

Background and Introduction:

Urinary retention is a known complication following surgical procedures, with a theoretical increased risk in patients receiving neuraxial anesthesia due to a decreased ability to sense bladder distension. Urinary retention is associated with adverse events including bladder atony, increased post void residuals, and postoperative urinary tract infection. Treatment of urinary retention involves intermittent or indwelling urinary catheter placement, both of which are associated with an increased prevalence of postoperative urinary tract infection.²

There currently is no consensus whether the use of a urinary catheter in elective joint arthroplasty with neuraxial anesthesia decreases the risk of urinary retention. The prevalence of retention reported in the literature varies widely with reports anywhere from 0% to 75% in patients with early removal of a catheter or after procedures performed without a catheter.

At Rush University Medical Center currently, all patients undergoing primary total joint arthroplasty receive neuraxial anesthesia preoperatively and have short term indwelling urinary catheter placed intraoperatively. The urinary catheter is removed when the patient arrives on the orthopedic floor and the Rush urinary retention protocol is followed.

The need for routine use of indwelling urinary catheters was previously investigated in a randomized controlled trial by Miller et al in 2013 in patients undergoing total hip arthroplasty. They found a 2.8% rate of urinary retention in patients who received a urinary catheter and a 9.7% rate in patients who did not. Although this did not demonstrate statistical significance (P 0.07), they concluded that a routine indwelling urinary catheter is not required. However, Miller et al provided a fairly large time span for urinary catheter use ("removal within 48 hours") and failed to provide any temporal data regarding duration of use. With this in mind, our study will further investigate this conclusion with a goal to identify if routine use of a urinary catheter that is removed on the same day of surgery decreases postoperative urinary retention in patients undergoing elective inpatient total joint replacement.

Study Design

ORA: 19123101-IRB03 Date IRB Approved: 2/21/2020 Amendment Date: 10/7/2020

Prospective, multi-surgeon, single institution, randomized controlled trial

Inclusion Criteria

Any patient >18 years of age scheduled for an inpatient primary hip or knee replacement

Exclusion Criteria

- 1. Patients with a known history of prostate, urological or kidney surgery
- 2. Patients where close monitoring of urine output are necessary during the perioperative period (renal disease, renal failure, chronic indwelling urinary catheter)
- 3. Patients with a history of urinary incontinence
- 4. Patients undergoing a revision total knee or total hip arthroplasty
- 5. Patients requiring indwelling continuous epidural anesthesia
- 6. Patients with a preexisting urinary tract infection, as diagnosed on preoperative screening.
- 7. Patients unable to void prior to surgery as required by anesthesia.

Treatment Groups:

Group 1 (Control): Short term urinary catheter- Patient will receive a urinary catheter at the time of the surgery. The urinary catheter will be removed upon arrival to the orthopedic floor post operatively. Patients will subsequently be monitored for urinary retention according to the Rush University Medical Center urinary retention protocol.

Group 2 (Experimental): No urinary catheter- Patients will not receive a urinary catheter at time of surgery. They will be monitored for urinary retention according to the Rush University Medical Center urinary retention protocol

Sample Size Calculation

Based on a randomized controlled trial published by Miller et al in 2013, to detect a clinically significant difference of 7%, we would need 194 patients per group, or 388 patients. Assuming a drop-out rate of 10%, a total of 432 patients will be required. An interim analysis will be performed once half of this total is enrolled.

Urinary retention protocol:

Patients will be monitored closely for urinary retention according to current Rush University Medical Center Urinary Retention Protocol. After removal of catheter (control group) or from arrival in PACU (experimental group), patients will be given 4 hours to void a volume corresponding to 30ml/hour. If the patient fails to do so, they will be bladder scanned. Bladder scan results of 450ml or greater will result in one time straight catheterization.

If bladder scan shows 150 ml to 349 ml of urine, patients will be given an additional 4 hours to void and a repeat bladder scan will be performed. If unable to void at this point and/or bladder volume is >450, patient will receive a one time straight catheterization.

If bladder scan shows 350 ml to 449 ml of urine, patients will be given an additional 2 hours to void and a repeat bladder scan performed. If unable to void at this point and/or bladder volume is >450, patient will receive a one time straight catheterization.

If patients require a straight catheterization, they will be monitored with bladder scan according to protocol and a second straight catheterization will be performed if necessary. At time of second straight catheterization, a urinalysis will be sent. If patient requires a third straight catheterization, a urology

ORA: 19123101-IRB03 Date IRB Approved: 2/21/2020 Amendment Date: 10/7/2020

consult will be placed according to protocol and patient will either receive an indwelling urinary catheter or intermittent straight catheterization with urology follow up.

Demographics, Patient Specifics

Age, sex, short form 12 scores, ASA score, medical co-morbidities, weight, height, length of hospitalization, BMI, history of benign prostatic hypertrophy, presence of preoperative urinary tract infection (diagnosed during preadmission testing), intravenous fluids given during surgery, operating room time, estimated blood loss, length of hospital stay, discharge destination (home versus rehabilitation facility), time to mobilization postoperatively, and length of urinary catheter usage.

At the time of enrollment in the study, patients will be given a urinary history questionnaire known as the International Prostate Symptom Score (I-PSS) and be asked about history of urinary retention, history of incontinence, and history of polyuria to screen for preexisting urinary issues. Existing pre-operative laboratory testing will be abstracted from the subjects' medical record.

Patients will receive standardized multimodal analgesic regimen that is utilized at Rush University Medical Center for patients undergoing a total joint replacement for perioperative and postoperative pain management. Modifications will be made on a case by case basis as is currently the standard practice (for example, allergy, intolerance, or medical contraindication such as acute kidney injury to NSAID use)

Outcome Measurements:

- 1. Episodes or urinary retention, defined as necessitating 2 straight catheterizations or placement of an indwelling urinary catheter.
- 2. Number of straight catheterizations and volume of urine
- 3. Episodes of indwelling urinary catheter placement in the postoperative course
- 4. Urinary tract infections
 - a. Diagnosed via urinalysis at time of second straight catheterization or urinary placement
 - b. Patients will be asked via questionnaire the following at time of initial follow up to screen for possible urinary tract infection. If screen positive, will order urinalysis and urine culture.⁶
 - Have you had any pain with urination?
 - Have you had an increase in urinary frequency?
 - Have you noticed any lower abdominal pressure with urination?
 - Have you noticed any changes in the color or smell of urine?
- 5. Patient satisfaction (HCAHPS survey) to be administered at initial follow up visit
- 6. Patients who receive a straight catheterization or placement of a urinary postoperatively will be asked via questionnaire a modified version of survey published by Darbyshire et al.⁷
 - a. Was placement of the catheter painful?
 - b. Was placement of the catheter embarrassing?
 - c. Did you know why you were catheterized?
 - d. Did the doctor or nurse talk you through why you were being catheterized?
- 7. Acute periprosthetic joint infections

Risks, Benefits

All surgical patients are at risk of developing urinary retention. To minimize adverse events associated with urinary retention, all patients will be closely monitored according to the Rush University Medical center urinary retention protocol.

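### Does the plan need a rule, fixed in advance, for reading a non-significant result against its 7-point difference?

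*Combined protocol and SAP*

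**What the plan says.** The Hypothesis section is directional: "We hypothesize that the routine use of a short term indwelling urinary catheter will decrease the rate of urinary retention" relative to no catheter. The Background and Introduction section describes an earlier randomized trial in hip arthroplasty with retention of 2.8% with a catheter and 9.7% without, and remarks: "Although this did not demonstrate statistical significance (P 0.07), they concluded that a routine indwelling urinary catheter is not required". The protocol's stated criticism of that trial concerns how long catheters stayed in, not the inference drawn from P 0.07. It then states its own aim: "our study will further investigate this conclusion with a goal to identify if routine use of a urinary catheter". The rest of that sentence makes the question whether such a catheter, taken out on the operation day, lowers retention after elective inpatient joint replacement.

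The same section says that all primary arthroplasty patients at the site now receive a catheter. Treatment Groups lists "Group 2 (Experimental): No urinary catheter". Sample Size Calculation plans "to detect a clinically significant difference of 7%, we would need 194 patients per group, or 388 patients", raised to 432 for 10% drop-out, with an interim analysis at half of enrolment. There is no statistical analysis section. Test, alpha, power, effect measure, interval, interim rule and reading of a null result are all unstated.

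**The concern.** A non-significant p-value does not show that a difference is small. The plan calls 7 points clinically significant but uses that figure only to size the trial. Nothing separates a null result whose interval lies below 7 points from one whose interval still contains 7.

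The setting makes this more than a formality. Catheters are routine at the site and omitting them is the experimental arm, so a null result bears on practice. The precedent that the protocol builds on drew a practice conclusion from P 0.07 with an observed difference of 9.7 − 2.8 = 6.9 points, almost exactly this plan's own threshold. If that step were repeated here, an inconclusive trial could be cited as evidence that catheters can be dropped.

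**Working it through.** **Inputs.** Rates of 2.8% and 9.7% come from Background and Introduction; 7 points, 194 per group and 10% drop-out come from Sample Size Calculation. Two-sided alpha 0.05 and 80% power are assumed, because the documents state neither. All calculations assume one final analysis with 194 per group and no stopping at the interim.

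**The plan's own figure.** n = [1.960·√(2p̄(1−p̄)) + 0.842·√(p₁(1−p₁)+p₂(1−p₂))]² / (p₂−p₁)².

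- Rates rounded to 3% and 10%, p̄ = 0.065: [1.960·0.3486 + 0.842·0.3451]² / 0.07² = 0.948/0.0049 = 193.5, so 194 per group.
- Unrounded 2.8% and 9.7%: 193 per group.
- 388/0.90 = 431.1, so 432.

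The figures reproduce as an ordinary superiority calculation, which supports the assumed alpha and power.

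**Can both kinds of null result occur?** Take the difference as no catheter minus catheter, with a Newcombe 95% interval: upper limit = d + √[(u₁−p₁)² + (p₂−l₂)²]. Here p₁ and its Wilson upper limit u₁ belong to no catheter, and p₂ and its Wilson lower limit l₂ to catheter. Suppose 5 of 194 catheter patients (2.6%) have retention, so p₂ = 0.0258 and l₂ = 0.0111.

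- 10 events without catheter: d = 0.0258; 0.0258 + √[(0.0923−0.0515)² + (0.0258−0.0111)²] = 0.069; p = 0.19. Seven points excluded.
- 11 events: d = 0.0309; upper limit 0.075; p = 0.13. Not excluded.
- 13 events: upper limit 0.088; p = 0.053. Not excluded.

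One event can separate the two.

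**How often?** Exact summation over both binomials, with the uncorrected two-proportion z test:

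| True rates, catheter / none | Non-significant | Non-significant, upper limit ≥ 7 points (all trials) | Share of non-significant results |
|---|---|---|---|
| 2.8% / 9.7% | 17.2% | 14.6% | 85% |
| 2.8% / 6.3% | 62% | 29% | 47% |
| 3% / 3% | 95% | 3% | 3% |
| 6% / 6% | 95% | 18% | 19% |
| 10% / 10% | 95% | 36% | 38% |

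The third column is the more useful one. The 85% is nearly built in: when the true difference is 6.9 points, an interval that covers zero will usually cover 7 as well. The 10% row exceeds the higher planning rate of 9.7%. Its support is the literature range in Background and Introduction ("reports anywhere from 0% to 75% in patients with early removal of a catheter", or without a catheter), which is not tied to this trial's definition of retention as two straight catheterizations or an indwelling catheter.

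**Does the plan commit to a wrong reading?** Purpose asks whether the catheter decreases retention; Hypothesis says that it will; the goal sentence that mentions the earlier conclusion ends by asking the same thing; the sample size is for detecting a difference. No sentence says that non-significance will be read as showing that a catheter is unnecessary. Naming no catheter as the experimental arm marks a departure from current practice and does not state a non-inferiority aim.

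**The case for a change.** The best case for a change is that it would be almost free. Reporting the risk difference with an interval, and saying beforehand that a null result reaching 7 points is inconclusive, needs no extra patients and leaves the test alone. Such a statement is most credible when made before the data are seen. Naming a test and an alpha would not supply it. The trial also enrols knee as well as hip patients, so rates may differ from the earlier trial's.

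Most of this stands as good reporting practice, and the omission and the figures are not in dispute. It does not show a fault in what the plan specifies. The harm needs a further step, reading non-significance as proof of no need, that the plan does not take. The documents do not say that a p-value alone will be reported, so the most one can say is that the two kinds of null result could be reported alike. The omission is also one line of an analysis section that is wholly absent, not a separate flaw.

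Using 7 points as a reading threshold has its own limit: the figure was chosen to size the trial and nearly equals the earlier observed 6.9, so it is not a justified non-inferiority margin. A formal claim at that margin (one-sided 0.025, 80% power, normal approximation) would need about 289 per group at a common rate of 10%, against 194 planned.

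**Conclusion.** No change to the plan follows. The trial is a coherent superiority comparison, and its sample size reproduces as one. No stated rule, number or analysis gives a wrong answer when followed. What is missing is a reporting detail that an analyst can fill sensibly with an estimate and a confidence interval, which lets any reader see whether 7 points is excluded.

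The chance of a null result that leaves 7 points open is about 15% at the planning rates. With equal true rates it runs from 3% (both 3%) through 18% (both 6%) to 36% (both 10%). These figures assume a two-sided 0.05 test, 194 analysed per group, a Newcombe interval and no interim stopping; if the interim look spends alpha, the interval level and the probabilities shift. The matter would weigh more if the documents stated that a null result establishes that catheters are unnecessary. They do not.

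### Does the missing step for a bladder scan below 150 ml leave the urinary retention outcome open to different readings by arm?

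*Combined protocol and SAP*

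**What the plan says.** The Urinary retention protocol section sets out monitoring "according to current Rush University Medical Center Urinary Retention Protocol". The clock starts at catheter removal in the control arm and at arrival in the recovery unit (PACU) in the no-catheter arm. From then, "patients will be given 4 hours to void a volume corresponding to 30ml/hour". A patient who does not manage this is scanned, and the printed actions are:

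- 150 to 349 ml: "If bladder scan shows 150 ml to 349 ml of urine, patients will be given an additional 4 hours to void", followed by a repeat scan.
- 350 to 449 ml: two more hours, followed by a repeat scan.
- At the first scan, "Bladder scan results of 450ml or greater will result in one time straight catheterization".
- At the repeat scan in either middle band, "If unable to void at this point and/or bladder volume is >450, patient will receive a one time straight catheterization".

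No action is printed below 150 ml. After a first straight catheterization, "they will be monitored with bladder scan according to protocol and a second straight catheterization will be performed if necessary".

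Outcome Measurements, item 1, counts urinary retention as "defined as necessitating 2 straight catheterizations or placement of an indwelling urinary catheter". It has no time window. Item 2 records the number of straight catheterizations and the urine volume.

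**The concern.** The voiding test and the scan bands do not meet. The test threshold is 120 ml and the lowest band begins 30 ml higher, so a patient can fail the test and then scan at a value for which the page gives no instruction. The route to a catheter for inability to void is printed only inside the two middle bands.

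Outcome 1 consists entirely of catheterizations, and the urinalysis in item 4a is tied to the second one. What staff do with a low scan could therefore affect who becomes an event.

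The gap might also fall unequally. A control patient starts the clock with a drained bladder. A no-catheter patient starts it with whatever has collected since the pre-operative void required by exclusion 7. The same urine output could put the first patient in the gap and the second in a printed band.

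Two smaller points sit alongside. The text does not say when the clock restarts after a catheterization, and the upper threshold is worded in two ways.

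**Working it through.** **Inputs from the Urinary retention protocol section:** 30 ml/hour; 4 hours; bands at 150–349, 350–449 and 450 ml or more; the two clock starts. **Assumed, because the documents give no figure:** nothing is voided; output is constant; the bladder is empty after any catheter; the clock restarts at each catheterization; the no-catheter patient reaches PACU t = 1 to 4 hours after the pre-operative void.

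**Where the gap lies.** The voiding test is 30 × 4 = 120 ml, and 150 − 120 = 30 ml. From an empty bladder with nothing voided, reaching 150 ml at 4 hours needs 150/4 = 37.5 ml/hour. Patients who void a little can also be in the gap: a void just under 120 ml with a scan just under 150 ml means output just under 270 ml in 4 hours (270/4 = 67.5 ml/hour).

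**First scan at 30 ml/hour, nothing voided.** Control: 120 ml, no printed step. No-catheter: 30 × (4 + t), all in the 150–349 band. The gap in that arm applies below 150/(4 + t).

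| t (hours) | No-catheter scan (ml) | Gap applies below (ml/hour) |
|---|---|---|
| 1 | 150 | 30 |
| 2 | 180 | 25 |
| 3 | 210 | 21.4 |
| 4 | 240 | 18.75 |

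So the first scan can differ by arm.

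**Does outcome 1 differ?** Take three ways of handling a scan below 150 ml, at 30 ml/hour with nothing voided, in hours on each arm's own clock. They are used only to test sensitivity; none is proposed as a rule.

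| Handling of a low scan | Control: 1st, 2nd catheterization | No-catheter: 1st, 2nd | Outcome 1 |
|---|---|---|---|
| A. As the 150–349 band | 8, 16 | 8, 16 | both arms |
| B. Wait 4 hours, rescan, then apply the bands | 12, 24 | 8, 20 | both arms |
| C. No further step | none | 8, none | neither arm |

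Under B, control scans 120 ml at 4 hours and 240 ml at 8 hours, is catheterized at 12, and repeats the cycle to 24. The no-catheter patient is in a band at the first scan and is catheterized at 8; the bladder is then empty, so the same 12-hour cycle ends at 20.

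The reason is general under these assumptions. After a first catheterization both arms start from an empty bladder, so the rule that leads to the second one acts alike. At 37.5 ml/hour, and at 40, all three handlings give 8 and 16 hours in both arms.

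**The 450 ml wording.** The first-scan rule includes exactly 450 ml and the repeat-scan rule does not. At the repeat scan, a patient unable to void is catheterized whatever the volume. The difference therefore touches only a patient who has voided by then and scans at exactly 450 ml.

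**The case for a change.** The best case for a change is that nobody reading this document can tell which rule governed the main outcome. The hospital protocol is cited only as current, with no date or version, and could have changed during enrollment. The listed variables name no scan times, scan volumes or reasons for catheterization, so the question could not be settled afterwards from them.

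Events may also be few. If the rates cited from the earlier hip trial applied, 194 per group would give 194 × 0.028 ≈ 5 and 194 × 0.097 ≈ 19 events. Three reclassified patients in one arm would move its rate by 3/194 ≈ 1.5 percentage points, against a target difference of 7.

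Timing could also turn into status. If voiding returns, or the patient goes home, between 16 and 24 hours, the handling of a low scan would decide whether a second catheterization happens.

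Much of this stands as description. The gap is on the page, the undated citation is loose, and the last argument cannot be excluded. But nothing in the documents says that three patients, or any number, would be reclassified. Nor does anything suggest that low scans would be handled differently by arm. The unequal first scan comes mainly from the different clock starts and starting bladder volumes, which would remain if every scan value had a printed step.

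**Conclusion.** No change to the plan follows. The observation is correct: no step is printed below 150 ml, and no other section supplies one. It is a missing detail in a summary of a procedure that exists elsewhere. Background and Introduction, Treatment Groups, the Urinary retention protocol section and Risks, Benefits all refer to the hospital's own retention protocol, and Background describes it as already in use. Both arms are managed under it. No further step for a patient who has voided nothing (handling C) also sits poorly with a text that promises close monitoring in two places.

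The likely size is small or unknown. The 30 ml/hour is the least a patient should void, not a forecast of urine production, so the 120 ml scan is one scenario. Exclusion 2 removes renal disease and renal failure, which makes output held that low for 16 to 24 hours harder to assume. In the scenario worked through, the handling of a low scan never separates the arms on outcome 1; the only difference in counts is none against one straight catheterization in item 2, under handling C. This rests on constant output, no return of voiding, and a clock that restarts at each catheterization. The share of patients who meet the gap cannot be had from the documents.

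The two wordings at 450 ml are a clerical slip. They and the printed bands must be reconciled with the hospital text, and the clinical content is for the investigators. No printed rule has been shown to give a wrong result, and no analysis or sample size depends on the answer.

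### One UTI outcome, two routes: urinalysis alone early after surgery (4a), symptom-triggered urinalysis with culture at follow-up (4b), and no stated result that counts as a UTI

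*Combined protocol and SAP*

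**What the plan says.** Outcome Measurements, item 4, has one heading for urinary tract infections and two entries below it.

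- **4a:** "Diagnosed via urinalysis at time of second straight catheterization or urinary placement". No culture, symptom criterion or positivity threshold is given. The section on the urinary retention protocol agrees: "At time of second straight catheterization, a urinalysis will be sent". It mentions no culture either.
- **4b:** "Patients will be asked via questionnaire the following at time of initial follow up to screen for possible urinary tract infection". Four symptom questions follow. The consequence is "If screen positive, will order urinalysis and urine culture". No day or window is given for this visit.

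Neither entry says which laboratory result makes a case. The document does not say whether 4a and 4b are added together or reported apart.

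Two other provisions bear on the point. Exclusion criterion 6 removes "Patients with a preexisting urinary tract infection, as diagnosed on preoperative screening", without describing the screening test or its timing. Outcome item 1 defines retention as two straight catheterizations or an indwelling catheter, which are the same events that trigger the 4a urinalysis.

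**The concern.** The two routes do not measure the same thing. A patient who reaches 4a can be called a UTI on a urinalysis alone. A patient who reaches 4b has first reported symptoms and then has a culture as well. The 4a specimen is also taken soon after surgery, from a bladder that has just been catheterized and usually not for the first time. An abnormal urinalysis in that setting may reflect instrumentation, or bacteria already present before surgery, rather than a postoperative infection.

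The Background names postoperative UTI as a harm of retention and of the catheterization used to treat it, so readers will want to compare UTI between arms. Only patients who meet the retention outcome receive the 4a test, and the hypothesis is that the no-catheter arm has more of them. Any unconfirmed positives would therefore fall mainly on that arm.

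**Working it through.** **1. The plan's own figure.** Sample Size Calculation states 194 per group, 388 in total, and 432 with 10% dropout. Alpha and power are not stated. Assuming two-sided 5% and 80%, with pooled variance and no continuity correction, 2.8% versus 9.7% gives 193 per group and 3% versus 10% gives 194. For dropout, 388 / 0.90 = 431.1, or 432 when rounded up to two equal groups. The stated size is reproduced, and 194 per arm is used below.

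**2. When the 4a specimen is taken.** The inputs are in the urinary retention protocol. The clock starts at catheter removal (control) or PACU arrival (no catheter), and then "patients will be given 4 hours to void a volume corresponding to 30ml/hour". After that, "Bladder scan results of 450ml or greater will result in one time straight catheterization". A scan of 350 to 449 ml adds 2 hours and a scan of 150 to 349 ml adds 4 hours.

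| Event | Hours from clock start | Basis |
|---|---|---|
| First straight catheterization | 4 + 0, 2 or 4 = 4, 6 or 8 | Stated windows |
| Second | 4 + 4 = 8 up to 8 + 8 = 16 | Assumes the whole cycle restarts |
| Third-catheterization stage, where an indwelling catheter may be placed | 8 + 4 = 12 up to 16 + 8 = 24 | Same assumption |

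The two 4a triggers together span 8 to 24 hours. The restart is an assumption, because after the first catheterization the text refers only to monitoring under the protocol and gives no hours. If the gap to the second were only 2 hours (illustrative), the second would fall at 6 to 10 hours. The upper end is not a ceiling either: no rule covers a scan below 150 ml.

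**3. How many patients reach 4a.** The Background gives retention of 2.8% with a catheter and 9.7% without, from the cited 2013 randomized trial in hip arthroplasty. It is assumed that these rates apply here under this protocol's retention definition.

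- Control: 194 x 0.028 = 5.4
- No catheter: 194 x 0.097 = 18.8
- Total: 24.2 of 388
- Ratio: 9.7 / 2.8 = about 3.5

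**4. What cannot be computed.** If a fraction f of 4a urinalyses were positive without infection, and f were equal in both arms, the no-catheter arm would gain (18.8 - 5.4) x f = 13.4 x f more false UTIs than control. The documents give no value for f and no expected true UTI rate, so neither the number of false UTIs nor their share of all UTIs follows from the plan.

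**The case against.** The strongest reply is that the document lacks a case definition and does not set two conflicting ones. That is largely fair for 4b, where the tests are ordered after a positive screen and nothing says a positive culture is required. It is less fair for 4a, where the wording makes urinalysis the means of diagnosis.

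Other parts of the reply also stand:

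- UTI is one of seven unranked outcomes. Purpose, hypothesis and sample size concern retention only, and nothing says UTI is the outcome against which a retention benefit will be weighed.
- Pre-existing UTI is excluded, preoperative UTI status is recorded and preoperative laboratory results are abstracted. This reduces the problem of bacteriuria already present but does not remove it, since the screening test and its date are not described.
- A symptom requirement at 4a would be hard to meet. The plan's symptom questions mostly concern urination, and the 4a patient has recently had neuraxial anesthesia and is not voiding adequately.

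A reader might also infer that 4a samples are all same-day, within a printed 8 to 16 hours. The interval is derived and not printed, it omits the catheter-placement trigger, and it can cross midnight. A reader might infer that a 4a result is too early to reflect any catheter effect. The documents do not support this: control patients had a catheter at surgery, and a first straight catheterization precedes the second in either arm.

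**Conclusion.** The point holds as a defect in outcome definition. One UTI heading covers two routes that differ in test, symptom requirement and timing, and neither states what counts as a case. At the cited rates about 5 control and 19 no-catheter patients of 194 per arm would be exposed to the less specific route. That imbalance rests on the cited retention rates carrying over. The 8 to 24 hour timing rests on the scan cycle restarting.

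Two stronger conclusions should not be drawn. A reader might infer that false positives make up a large share of all UTIs, but that needs a false-positive rate and a true UTI rate that the documents do not contain. A reader might also infer that the two routes are pooled into one count. The shared heading suggests this but no text says so. The retention comparison and the sample size are unaffected. This is an inexpensive improvement to one listed outcome.

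**What to change.** For outcome classification, amend item 4 as follows:

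1. Add a urine culture on the specimen already collected at 4a.
2. State one culture criterion, including what result is positive, and use it to count a UTI in both routes.
3. Record a positive urinalysis with a negative culture as a laboratory finding, not a UTI.
4. Report 4a and 4b events separately by arm, with the number tested by each route.
5. Do not make symptoms mandatory for 4a.

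Step 4 is needed even with culture, because 4a testing will still occur only in patients who meet the retention outcome. Culture makes the result more specific but does not equalize who is tested.

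The cost is a wording change and about 24 cultures in 388 patients. If all 432 enrolled are followed, 216 x (0.028 + 0.097) = 27. The UTI count is likely to be lower. The change concerns which events are counted and takes no position on how any result is managed clinically.
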